# 8.5.6 Spirometry

Spirometry testing will be performed according to the ATS guidelines (Miller et al 2005); (Culver et al 2017) at screening to assess patients' eligibility for the study and as detailed in the Assessment schedule (Section 8.1).

The spirometry equipment will be supplied to each site for the study. The same spirometry equipment should be used for all assessments performed by a subject. A limited number of staff, as designated by the investigator, will evaluate all patients at all visits throughout the entire trial. Where possible the same technician should perform all maneuvers for an individual subject. All staff conducting the spirometry tests must have received appropriate training which must be documented. Information on the procedure can be found in the SOM.

16 according to the schedule on enrolled patients and the results compared to baseline findings using centralized quantitative reading. Detailed information will be provided in a separate [F]FDG-PET/CT imaging manual. Total injected activity and body weight will be recorded and used to compute standardized uptake values (SUVs). The total radiation dose for all PET/CT scanning (excluding HRCT) in this protocol will be maximally 11 mSv (or 16 mSv if [F]FDG injected dose is 350 MBq). In all subjects, the baseline and follow-up PET/CT scan (at week 16) should be performed where possible on the same scanner.

Confidential

Refer to the Imaging Acquisition Guidelines and Imaging Investigator Site Operations Manual for [F]FDG-PET/CT.

The coded medical images will be used primarily for analysis as described in this protocol; however, the images may also be used for the development and evaluation of new analysis methods directly related to the area of research that this study covers. Incidental findings are beyond the scope of central imaging vendor. If an investigator/radiologist recognizes any incidental finding in the images during the course of conducting the clinical trial, the investigator should follow up as part of his/her duty of care to ensure the safety and wellbeing of the participant.

# 8.6 Safety

Safety assessments are specified below; methods for assessment and recording are specified in the SOM, with the Assessment schedule (Section 8.1) detailing when each assessment is to be performed.

## 8.6.1 Adverse Events

Safety assessments are specified below; methods for assessment and recording are specified in the SOM, with Assessment schedule (Section 8.1) detailing when each assessment is to be performed. The safety assessments include:

- Adverse events, vital signs, physical exams, safety labs (hematology, chemistry, urinalysis), and electrocardiogram (ECG).
- CSE (Section 8.6.3)

# 8.6.2 Body Temperature

Body temperature will be measured at multiple time points during the study. The same method of measurement should be used throughout study. Please refer to the Assessment schedule (Section 8.1).

# 8.6.3 Clinical Chemistry

The fasting chemistry panel will include: albumin, alkaline phosphatase, total bilirubin, calcium, chloride, serum bicarbonate, creatinine, creatine kinase (CK), aspartate aminotransferase (AST), alanine aminotransferase (ALT),  $\alpha$ -amylase,  $\gamma$ - glutamyltransferase (GGT), glucose, sodium, potassium, inorganic phosphorus, total protein, lactate dehydrogenase (LDH), magnesium, blood urea nitrogen (BUN), uric acid, lipase and serum ketones.

If the total bilirubin concentration is increased above 1.5 times the upper limit of normal, direct and indirect reacting bilirubin should be differentiated.

Please refer to the Assessment schedule (Section 8.1).

# 8.6.4 Blood Pressure and Pulse Rate

Blood pressure and pulse rate will be recorded at multiple time points during the study. Please refer to the Assessment schedule (Section 8.1) and the SOM for additional information.

## 8.6.5 ECG evaluation

Full details of all procedures relating to the ECG collection and reporting are contained in the SOM.

ECG parameters will include: PR interval, QRS duration, heart rate, RR interval, QT interval, QTcF. The Fridericia QT correction formula (QTcF) calculated with the RR interval expressed in seconds should be used for clinical decisions.

Clinically significant abnormalities must be reported in the AE CRF.

## 8.6.6 Hematology

The hematology panel will include: hemoglobin, hematocrit, red blood cell (RBC) count, white blood cell (WBC) count with differentials (e.g. neutrophils, basophils, eosinophils, monocytes, lymphocytes) and platelet count will be measured. Please refer to the Assessment schedule (Section 8.1) and SOM.

## 8.6.7 **Pregnancy and assessments of fertility**

## Pregnancy Testing

All pre-menopausal women who are not surgically sterile will have pregnancy testing. Serum pregnancy testing is required at Screening (V1) and EOS#1 (V399). Urine pregnancy testing is required at V201, V202, V203, V204, V299, V301, V302 and for an additional 8 weeks (V401, and EOS#2 V499; for all urine pregnancy testing, record the results in source documentation at the study site).

See the Assessment schedule (Section 8.1), for timing of the protocol required pregnancy testing\*. A positive urine pregnancy test requires immediate interruption of study treatment until serum  $\beta$ -hCG is performed and found to be negative.

\*Additional pregnancy testing might be performed if requested per local requirements.

Refer to Section 9.6 for details on Reporting Pregnancy.

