## Run-in Epoch

[figure not shown]
A 6-week run-in epoch will commence on **Day -42**. First, eligible patients will discontinue methotrexate and azathioprine. Hydroxychloroguine will be allowed to continue as background therapy. Then, on **Day -28** (2 weeks after discontinuation of methotrexate or azathioprine), patients will undergo a full safety assessment, a "Clinical Status Evaluation (CSE)", and enter into a steroid (prednisone or equivalent; see Table 17-1-Appendix 3) titration algorithm. CSE will consist of a 6-minute walk test, spirometry assessments, and an assessment of dyspnea (Modified Medical Research Council [mMRC] breathlessness scale). The CSE serves as an additional safety evaluation and will serve to establish the patient's current clinical status (Clinical Status Determination [CSD]) as compared to their status at Day -42 (Figure 3-2). The CSE will be performed at each subsequent visit, prior to the titration of steroids, and the CSD will guide selection of the next dose of steroids (Figure 3-3). Steroid titration will continue through the run-in epoch: and steroid titration will also continue through the treatment epoch. Patients with CSD of "improved" or "stable" will decrease steroid dose by 1-step on the dosing scale (Figure 3-4). (Note: To prevent Addisonian crisis, steroids will not be tapered below a physiologic dose (2.5 mg/day); and steroid tapering will follow a very slow regimen, as per protocol – i.e., modest decreases in dose, no more frequent than every four weeks). Patients with CSD of "deteriorating" will be ineligible to continue the study (if "deteriorating" is determined during the run-in epoch); or they will increase their steroid dose by 1-step (if "deteriorating" is determined during the treatment epoch). [ $^{18}$ F]-FDG PET/CT will be performed prior to the first dose (**Day -2 (± 1**)) and again at the end of the treatment epoch (**Day 113**).

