- 15. Positive hepatitis B surface antigen (HBsAg) with concurrent negative hepatitis B surface antibody (anti-HBs); or positive total hepatitis B core antibody (anti-HBc) with concurrent negative anti-HBs; or positive hepatitis C antibody (anti-HCV) unless it can be documented that the patient has received highly-effective HCV-specific antiviral therapy, HCV RNA levels are measured, and HCV RNA is undetectable at least 12 weeks after the conclusion of HCV-specific antiviral therapy; i.e., any acute or chronic infection with hepatitis B or hepatitis C
- 16. Evidence of active or latent tuberculosis (TB) infection, as determined by Quantiferon test at screening (Note: if Quantiferon test is indeterminate, it may be repeated once. Two indeterminate Quantiferon tests will be considered as evidence of TB infection. Furthermore, after anti-TB treatment, patients with history of or latent TB may become eligible according to national guidelines)
- 17. Receipt of live/attenuated vaccine within a 1 month period before first dose of CMK389 (V201)
- 18. Contraindication to FDG-PET scan investigations such as severe claustrophobia or uncontrolled diabetes
- 19. History of confirmed malignancy of any organ system (other than localized carcinoma of the skin (for example: basal, squamous) or in situ cervical carcinoma), treated or untreated, within 5 years of screening, regardless of whether there is evidence of local recurrence or metastases
- 20. Pregnant or nursing (lactating) women, where pregnancy is defined as the state of a female after conception and until the termination of gestation, confirmed by a positive hCG laboratory test
- 21. Women of childbearing potential (WOCBP) (see definition below), unless they are using highly effective methods of contraception during dosing and for an additional 6 months after the last dose (infusion)

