### Page 58 Protocol No. CCMK389X2201

Confidential

Novartis	Confidential
Amended Protocol Version v08 (Clean)	

Page 59
Protocol No. CCMK389X2201

Epoch	Pregnancy Testing Period (WOCBP Only) 				
Visit Name	Pregnancy Testing (WOCBP Only)	End of Study #2			
Visit Numbers 	401	499			
Days	225 ±3	253 ±3			
Pregnancy and assessments of fertility	S 	S 			
Serious Adverse Event - Only Pregnancies Reported 	Х	X			
Study/Epoch completion information		X			

x Assessment to be recorded in the clinical database or received electronically from a vendor

S- source documentation at the study site

 Visit structure given for internal programming purpose only

 Unless specified otherwise, assessments at 0 min should be done pre-dose

 Can be done at Day -1 instead of Day 1 if needed.

 Determined by QuantiFERON TB-Gold test

 Serum pregnancy test

 Urine pregnancy test

 Chemistry panel must be done under fasting conditions at all visits

 Only for patients who don't have an historical chest x-ray within 12 months from screening

 HRCT at screening should be performed after all other screening assessments for eligibility. A historical HRCT obtained within 12 months prior to screening may be used instead and sent to the central reader for analysis.

 Fasting glucose and [F]FDG-PET/CT must be done on a different day than the other assessments of V299 or after all other V299 assessments are completed on the same day.

 The [F]FDG-PET/CT requires a blood glucose level below 11 mmol/L. The measurement is performed by finger prick at site before [F]FDG-PET/CT is performed

 Clinical Status Determination includes the following: 6-minute walk distance, FVC, FEV1 and mMRC dyspnea score. Complete the form (found in the SOM) and use as a guide for CSE

 Discontinue methotrexate and azathioprine

 Patients with CSD of "deteriorating" will be ineligible to continue the study (during the run-in epoch); or they will increase steroid dose by 1-step (during the treatment epoch). See study design Section 3.1

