#### 8.4.5 Inclusion / Exclusion criteria

The investigator must ensure that all subjects being considered for the study meet the inclusion and exclusion criteria. No additional exclusions should be applied by the investigator, in order that the study population will be representative of all eligible subjects.

Subject selection is to be established by checking through all inclusion/exclusion criteria at screening, V102 and V201. A relevant record (e.g. checklist) must be stored with the source documentation at the study site. Deviation from any entry criterion excludes a subject from enrolment into the study. The investigator or his/her deputy must promote compliance to inclusion/exclusion criteria for the duration of the study.

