### 9.6 **Pregnancy reporting**

Reproductive toxicity and teratogenicity data are not available for the investigational drug at this time, therefore no guidelines on therapeutic recommendations in case of pregnancy are available. This study enrolls women on highly effective birth control and who are considered not to be of childbearing potential, thus pregnancy is not an expected outcome for any female study participant. However, in the case that a pregnancy in a female study participant should occur, please follow the below reporting guidelines.

To ensure subject safety, each pregnancy occurring after signing the informed consent must be **reported to Novartis within 24 hours** of learning of its occurrence. The pregnancy should be followed up to determine outcome, including spontaneous or voluntary termination, details of the birth, and the presence or absence of any birth defects, congenital abnormalities, or maternal and/or newborn complications.

Pregnancy must be recorded on the Pharmacovigilance Pregnancy Form and reported by the investigator to the local Novartis Chief Medical Office and Patient Safety (CMO&PS) Department. Pregnancy follow-up should be recorded on the same form and should include an assessment of the possible relationship to the study treatment.

Any SAE experienced during the pregnancy and unrelated to the pregnancy must be reported on an SAE form.

The study drug must be discontinued though the subject may stay in the study, if she wishes to do so. All assessments that are considered as a risk during pregnancy must not be performed. The subject may continue all other protocol assessments.

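### No pregnancy test is required between screening and V201, so a baseline FDG-PET/CT on Day -3 or -2 rests on a test that is 40 to 68 days old

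*Protocol*

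**What the plan says.** Protocol Section 8.6.7 names the tests. For serum: "Serum pregnancy testing is required at Screening (V1) and EOS#1 (V399"). For urine: "Urine pregnancy testing is required at V201, V202, V203, V204, V299, V301, V302", followed by the two visits of the pregnancy testing period. The pregnancy row of Table 8-1 matches: serum at screening, nothing at V101, V102 or V199, first urine test at V201. Footnote 3 lets the V201 test move to Day -1, and no earlier. Section 8.6.7 adds that "Additional pregnancy testing might be performed if requested per local requirements".

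On imaging, Section 3.1 (Run-in Epoch) says that "PET/CT will be performed prior to the first dose", on Day -2 ±1, which is V199 in Table 8-1. Section 8.5.7 describes a scan from head to mid-thigh with a low-dose attenuation CT.

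Three further provisions bear on the point:

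- Section 8.4.5: "Subject selection is to be established by checking through all inclusion/exclusion criteria at screening, V102 and V201". Exclusion 20 in Section 4.2 treats pregnancy as "confirmed by a positive hCG laboratory test".
- Section 9.6, for a participant who becomes pregnant: "All assessments that are considered as a risk during pregnancy must not be performed".
- Table 8-1, footnote 11, sets a blood glucose limit for the scan: "The measurement is performed by finger prick at site before" the scan.

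**The concern.** The baseline PET/CT falls in the one stretch of the schedule with no pregnancy test: about six to ten weeks between screening and V201. A site that follows the protocol text alone can inject FDG and acquire the CT in a woman with an unrecognised pregnancy conceived in that interval. The V201 test, days later, could find the pregnancy and stop dosing, but only after the exposure.

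The other scans are mostly sequenced after a test. Footnote 9 puts a screening HRCT after all other screening eligibility assessments, hence after the serum test. Footnote 10 puts a same-day V299 PET/CT after the other V299 assessments, which include the urine test. The baseline PET/CT is the outlier, although its adult dose exceeds the HRCT maximum of 4 mSv and its field extends to mid-thigh. At stake is participant and fetal safety in a study-only procedure, not the analysis.

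**Working it through.** The plan states no figure for this interval, so there is none to reproduce. The check is day arithmetic on Table 8-1.

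**Inputs.** Screening: Day -70 to -43. V102: Day -28 ±1. V199 scan: Day -3, -2 or -1. V201 urine test: Day 1, or Day -1 under footnote 3. V204: Day 85 ±3 (82 to 88). V299: Day 113 ±3 (110 to 116). On re-screening (Section 8.3), earlier results count only if their windows are still met, so Day -70 remains the oldest usable test. All baseline days are negative, so the absence of a Day 0 does not matter.

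**Age of the last required test at the baseline scan** (scan day minus screening-test day):

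| Scan day | Shortest | Longest |
|---|---|---|
| -3 | -3 - (-43) = 40 | -3 - (-70) = 67 |
| -2 | -2 - (-43) = 41 | -2 - (-70) = 68 |
| -1, V201 test not done first that day | -1 - (-43) = 42 | -1 - (-70) = 69 |

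For Day -3 and -2 together the range is 40 to 68 days, because no required test can fall between screening and the scan. For Day -1 the gap closes only if the V201 test is brought forward to that day and done before the scan.

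**V102 eligibility re-check to scan.** Shortest -3 - (-27) = 24 days; longest -1 - (-29) = 28 days. No hCG test is scheduled with it.

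**Week 16 scan done on an earlier day than the V299 urine test.** The last required test is then the one at V204. Shortest 110 - 88 = 22 days. Longest: test on Day 116, so scan on Day 115 at the latest, 115 - 82 = 33 days.

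**Adult effective dose per PET/CT** (Sections 3.7 and 8.5.7). 4 + 1.5 = 5.5 mSv, consistent with 11/2 for two scans; at 350 MBq, 16/2 = 8 mSv. No fetal dose is given.

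**Expected undetected conceptions at V199.** Formula: n × 0.01 × days/365. The number of women of childbearing potential scanned is assumed to be 10 to 33 (33 is half of the 66 planned). Section 4.2 gives a failure rate below 1% for some contraceptive methods without a time unit; 1% per year is assumed for all.

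- n = 10: 10 × 0.01 × 40/365 = 0.011; 10 × 0.01 × 69/365 = 0.019
- n = 33: 33 × 0.01 × 40/365 = 0.036; 33 × 0.01 × 69/365 = 0.062

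**The case against.** The strongest objection is that a test may already be required elsewhere. The protocol leaves operational detail to the Site Operations Manual, and Section 8.5.7 refers PET/CT procedure to separate imaging manuals; a pre-injection pregnancy check could well sit there. That stands as a limit: the protocol text lacks the test, which does not prove that no site performs one. For the same reason the glucose comparison is only suggestive, since stating one pre-scan check does not show that others are missing from the manual. But Section 8.6.7 sends sites to the assessment schedule for test timing, so a required test should be visible or cited there.

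Second, other safeguards exist: contraception under exclusion 21 and Section 5.1, with reminders throughout the study (Section 5); the three-month stability rule for oral contraceptives; the open-ended exclusion of FDG-PET contraindications (exclusion 18); examinations at V101 and V102; and testing under local rules. They lower the risk, but none requires a test before injection. Exclusion 21 names dosing and the six months after it, not the run-in. The bar in Section 9.6 works only once the pregnancy is known.

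Third, the risk is very small, no stated maximum test-to-scan interval is breached, and the protocol is already at version 8, so a change helps only women not yet scanned. All of that stands and limits the priority. It does not remove the case for a very cheap precaution. The week 16 point is minor: 22 to 33 days is close to the four-weekly testing used during treatment.

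**Conclusion.** The concern holds. Section 8.6.7 and Table 8-1 agree with each other, so this is not a table-reading artefact: for a baseline PET/CT on Day -3 or -2, the last protocol-required pregnancy test is 40 to 68 days old. The absolute risk is small, about 0.01 to 0.06 undetected conceptions trial-wide, and that figure rests on the assumed count of women and the assumed annual failure rate. For a change adopted now it is an upper bound on the benefit, since some women may already have been scanned. Sample size, primary analysis and endpoints are untouched. It should be fixed because the exposure is largely avoidable at a visit that already takes place. Confidence is moderate, because the imaging manuals could not be checked.

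**What to change.** - **Table 8-1**, pregnancy row: add S with footnote 6 (urine test) at V199.
- **Section 8.6.7**: add V199 to the urine-test visits and state that the result must be negative before FDG injection. Keep the V201 pre-dose test.
- **If an imaging manual already requires a pre-scan test**, cite it in 8.6.7 instead.
- **Secondary, footnote 10**: for women of childbearing potential whose V299 scan is on an earlier day than the other V299 assessments, require a negative urine test on record before injection. Same-day V299 scans need no change.

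The cost is one urine test per woman of childbearing potential at V199, where a finger-prick glucose check already precedes the scan, plus one for any V299 scan done on an earlier day. The downsides are a little site time and a rare false positive that delays a scan until serum confirmation. A urine test can miss a very recent conception, so the risk is reduced, not removed. The change needs the approvals in Section 13.1 and can go into the next planned amendment.

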## Assessments of Fertility

Refer to Section 4.2 for criteria to determine women that are not of childbearing potential.

Medical documentation of oophorectomy, hysterectomy, or bilateral tubal ligation must be retained as source. Subsequent hormone level assessment to confirm the woman is not of childbearing potential must also be available as source documentation in the following cases:

- surgical bilateral oophorectomy without a hysterectomy
- reported 12 months of natural (spontaneous) amenorrhea with an appropriate clinical profile.

In the absence of the above medical documentation, FSH testing is required of any female subject, regardless of reported reproductive/menopausal status at Screening.

### 8.6.8 Physical Examination

A complete physical examination will include the examination of general appearance, skin, neck (including thyroid), eyes, ears, nose, throat, lungs, heart, abdomen, back, lymph nodes, extremities, vascular, and neurological. If indicated based on medical history and/or symptoms, rectal, external genitalia, breast, and pelvic exams will be performed.

Information for all physical examinations must be included in the source documentation at the study site. Clinically relevant findings that are present prior to signing informed consent must be recorded on the appropriate CRF that captures medical history. Significant findings made after signing informed consent which meet the definition of an Adverse Event must be recorded as an adverse event.

## 8.6.9 Urinalysis

A urine sample (approx. 30 mL) will be obtained midstream in order to avoid contamination with epithelial cells and sediments, and to allow proper assessments.

Semi-quantitative 'dipstick' evaluation of the urine for the following parameters will be performed centrally: specific gravity, pH, glucose, protein, bilirubin, ketones, nitrite, leukocytes and blood.

If the dipstick result is positive for nitrite, leucocytes and/ or blood, the sample will be sent for culture and for microscopic analysis of white blood cells, red blood cells and casts.

## 8.6.10 Body Weight and Height

Body weight and height will be recorded at multiple time points during the study. Refer to the Assessment schedule (Section 8.1).

